### 4.1. Treatment Assignment

Any subject meeting all inclusion and no exclusion criteria is eligible for enrollment in the study. Subjects are considered enrolled in the study once the informed consent form (ICF) and Health Insurance Portability and Accountability Act (HIPAA) form have been executed.

All subjects will receive a NW System (research phone, research watch, and NW proprietary application-set to either an active mode or a sham mode). 240 subjects will be enrolled into the study. Subjects will be randomly assigned to receive either the Active System or Sham System. There will be 120 subjects in each arm. None of the subjects will be aware of whether they have received an Active System or a Sham System. For further details of treatment assignment procedures, go to the “Randomization” section of this protocol.

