### 7.3. Sample Size Determination

A total of 240 veterans and active-duty service members will be enrolled (consented) into the study so that even with attrition of up to 50% of study subjects, we can ensure that the study is completed by a MINIMUM of  $n = 120$  participants (60 in each arm) to reach 90% power for rejecting the null hypothesis under the targeted benefit of  $\delta = \mu_{\text{Active}} - \mu_{\text{Sham}} = 3$  points with an equal standard deviation of  $\sigma = 5$  points in each of the two arms. Figure 1 (see below) depicts the power of the trial as a function of the true standardized reduction ( $\delta/\sigma$ ) in the population assuming we enroll and **retain** a MINIMUM of 60 participants in each arm of the proposed trial. If we get more than 60 participants (i.e. less than a 50% attrition rate) this will just make the study results even more powerful.

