#### **7.6. Secondary/Exploratory Analyses**

Secondary and Exploratory analyses will be carried out with appropriate regression modeling techniques and hypothesis tests. In particular, we will use longitudinal data analysis methods, such as generalized estimating equations and generalized linear mixed models, to assess temporal variation in the longitudinal outcome measures, and we will carry out two sample t-tests of the secondary hypotheses.

At the conclusion of the trial, the data will be assessed as both intention to treat (ITT) and per protocol. The effect sizes at the conclusion of the analyses will be compared using standard techniques. If the effect size of the per protocol analysis is greater than 10%, data will be reported as intention to treat to decrease probability of type I errors. Both analyses will follow the outline below:

Secondary outcomes, data will be presented as mean(standard deviation) or median (interquartile range), as appropriate for continuous variables. Categorical variables will be presented as frequency

(percentage). Continuous data will be assessed for normality, and transformed as appropriate (e.g. log transformation, square root transformation, etc.). Patient demographics and characteristics will be listed and compared. Continuous variables will be analyzed by category, intervention vs control, by two-sided t-test or Mann-U Whitney, as appropriate. Categorical variables will be compared by Chi-Square test or Fisher's Exact test as appropriate. Longitudinal data will be analyzed by repeated measures tests as appropriate for the variables.

Repeated measure ANOVA will be used to determine the difference in responses at the time points between groups for all survey types and questions, as appropriate. If determined inappropriate Poisson regression models will be used to determine the univariate, univariable, effect size.

Upon secondary outcomes analysis, multivariable, adjusted, models will be used to determine controlled effect sizes. Each variable with a p-value of 0.25 or less in standard distribution test will be included in the model. Backward stepwise regression modeling may be used to best fit the model.

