All measures used in this study will be evaluated using an intention-to-treat analysis; that is, all study participants completing the study will be included in the data analysis in the group to which they were assigned at enrollment. Additionally, a per-protocol analysis will be completed for all measures used in the study. For this analysis, use of the study device at least 50% of the study nights during the first 30 nights of the study will constitute adequate adherence to the study treatment.

The Trauma-Related Nightmare Scale questionnaire is not designed to produce a score when it is administered. The individual questions on this scale will be evaluated separately from one another.

Missing data is inevitable and can be handled in multiple ways. The data will need to be evaluated to determine the randomness of the missing data. First we will identify the distribution of the missing values and their impact then we will determine a path to deal with missing data. Depending on the impact of the missing values, we will omit participants without full data, omit missing values, impute missing values with the mean, or use multiple imputation.

Secondary and Exploratory analyses will be carried out with appropriate regression modeling techniques and hypothesis tests. In particular, we will use longitudinal data analysis methods, such as generalized estimating equations and generalized linear mixed models, to assess temporal variation in the longitudinal outcome measures, and we will carry out two sample t-tests of the secondary hypotheses. At the conclusion of the trial, the data will be assessed as both intention to treat (ITT) and per protocol. The effect sizes at the conclusion of the analyses will be compared using standard techniques. If the effect size of the per protocol analysis is greater than 10%, data will be reported as intention to treat to decrease probability of type I errors. Both analyses will follow the outline below:

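### The SAP's intention-to-treat set is a completers set, and neither the missing-data method nor the reported population is fixed in advance

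*SAP*

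**What the plan says.** The SAP's Data Analysis Plan states "All measures used in this study will be evaluated using an intention-to-treat analysis" and then explains the term: "all study participants completing the study will be included in the data analysis in the group to which they were assigned at enrollment". Protocol 7.6 also mentions ITT but does not define it, so the SAP's definition is the only one. It covers all measures, and therefore the primary PSQI comparison (Protocol 7.2) and the ESS and C-SSRS tests (Protocol 7.5). Neither document says whether completing means reaching Day 30, the end of the randomised phase, or Day 90, the end of the open-label extension.

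Protocol 7.3 enrols 240 people, counted at consent, to allow for completion by 120 "participants (60 in each arm) to reach 90% power for rejecting the null hypothesis", "even with attrition of up to 50% of study subjects". Protocol 4.1 says "There will be 120 subjects in each arm".

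On missing data, the SAP first examines how the gaps are distributed and what effect they have. Depending on that effect, "we will omit participants without full data, omit missing values, impute missing values with the mean, or use multiple imputation".

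A per-protocol analysis (device worn on at least half of the first 30 nights) is also planned. Both documents then add: "If the effect size of the per protocol analysis is greater than 10%, data will be reported as intention to treat".

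**The concern.** Completing happens after randomisation and may depend on treatment. Selecting on it gives up the balance that randomisation provides. The documents give reasons to expect loss that differs by arm. The device may wake the user or alarm falsely (Protocol 9.1.1), participants may stop wearing it if their sleep gets worse (9.1.3), and only the Active system vibrates overnight (2.3). Sham participants, who receive no intervention, may also leave for lack of benefit. Bias could therefore run either way, and the plan contains no analysis that would reveal it.

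Three further points follow.

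- ESS and C-SSRS are tested within the Active arm by one-sample tests. If people who worsen leave, the completers look safer, and no sham comparison offsets this.
- If completing means Day 90, someone with a valid Day 30 PSQI who leaves during the extension drops out of the primary analysis.
- The missing-data method, and possibly the reported population, are settled only after results are visible. The SAP does not say that the choice is made blind to allocation.

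At stake is the one-sided 2.5% error rate claimed in Protocol 7.2.

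**Working it through.** **1. The plan's own figure.** Inputs from Protocol 7.2 and 7.3: difference 3 points, SD 5, two-sided 0.05, 60 completers per arm.

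- SE = 5 × √(2/60) = 0.913.
- Power = Φ(3/0.913 − 1.96) = Φ(1.33) = 0.908; the exact t-test value is 0.903.
- With O'Brien-Fleming looks at 20, 40 and 60 per arm, simulated power is 0.903 and one-sided error 0.025.
- Enrolment: 120/(1 − 0.5) = 240.

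The arithmetic is right, but it describes completers.

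**2. Completers set with no true effect.** Assumptions, none from the documents: 120 randomised per arm, half retained in each, and a propensity to stay that correlates r with improvement in the Active arm only.

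- Shift = r × 5 × φ(0)/0.5 = r × 5 × 0.399/0.5 = 3.99r.
- One-sided error = 1 − Φ(1.96 − shift/0.913).

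| r (Active only) | Spurious benefit | One-sided error |
|---|---|---|
| 0.1 | 0.40 points | 6.4% |
| 0.2 | 0.80 points | 13.9% |
| 0.3 | 1.20 points | 25.8% |

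Simulation gives 14.1% and 24.8% for r = 0.2 and 0.3. Other cases:

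- 80% retained, r = 0.3 in Active only: shift 0.53 points, error 11.1% (simulated).
- r = 0.3 in both arms, 50% retained: error 2.4% (simulated).
- Dropout unrelated to outcome: 2.8% at 50% retained and 2.5% at 80% (simulated).
- r = 0.2 in Sham only: shift 0.80 points against Active, error 1 − Φ(1.96 + 0.80/0.913) = 0.2%.

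**3. Single mean imputation.** Suppose a fraction f of each arm is missing at random and is filled with the arm mean. The variance shrinks by (1 − f) while the apparent sample size is restored, so the calculated SE is (1 − f) times the true one. Two-sided error = 2[1 − Φ(1.96(1 − f))].

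- f = 0.2: 2[1 − Φ(1.568)] = 11.7%.
- f = 0.5: 2[1 − Φ(0.98)] = 32.7%.

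Filling with the overall mean leaves error near nominal but multiplies the estimated effect by (1 − f). At f = 0.5, 3 points becomes 1.5.

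**4. The 10% rule.** Two natural readings were simulated with 60 per arm and 60% to 80% adherent (assumed).

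- ITT is reported if the per-protocol effect exceeds the ITT effect by more than 10%, otherwise per-protocol. One-sided error is 1.2% to 1.3% without one-sided selection and 2.0% to 2.3% with r = 0.3 in Active only. Power falls from 0.91 to 0.69–0.82.
- ITT is reported if the two differ by more than 10% in either direction. Error is 2.0% to 2.5% and power 0.87–0.89.

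**5. All randomised participants.** SE at 120 per arm = 5 × √(2/120) = 0.645, treating every outcome as obtained.

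- 3 points for everyone: power 0.996.
- Half leave and gain nothing: effect 0.5 × 3 = 1.5 points, power Φ(1.5/0.645 − 1.96) = 0.642.
- Half leave and gain 1.5: effect 2.25 points, power 0.936.
- 20% leave and gain nothing: effect 2.4 points, power 0.961.

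**The case against.** The best defence is that the plan keeps more people under assessment than the word completing suggests. Stopping wear is not leaving the study. Protocol 6.15 pays for continued participation separately from wear, staff contact non-wearers (2.3), and Day 30 assessments may be done by phone or mail (6.12). The per-protocol wear threshold implies that completers who wear the device less remain in the ITT set. This stands, and it may keep attrition well under the ceiling. It does nothing for participants who do leave.

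The 50% is a tolerated maximum among consented subjects. Consent precedes the eligibility decision at Visit 1, so some of the loss may come before randomisation, although Protocol 4.1 puts 120 in each arm. The documents do not settle this, so a reader should not infer that half of those randomised will be lost.

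Mean imputation is one of four permitted options, beside multiple imputation; it is not the designated fallback. Its 33% error needs arm-specific means with half the values imputed. That cannot occur together with a completers set, from which those participants are already excluded, so the 26% and 33% figures must not be combined.

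A reader might also infer that the 10% rule lets the more favourable population become the headline. Its only stated trigger leads to ITT, and neither natural reading raises type I error. Reporting whichever analysis is significant would give 3.2% to 4.1%, or up to 13% with Active-only selection, but the text does not prescribe that. The rule sits with the secondary analyses, and whether it reaches the primary test is unclear.

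Protocol 7.2 does mention repeated-measures testing of PSQI change, which could use Day 14 data, but it leaves the form to the statistician's later judgement.

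**Conclusion.** The core defect stands and should be corrected before analysis: followed as written, the plan produces a completers analysis labelled intention-to-treat, for the primary outcome and for both safety scales.

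The size of any bias cannot be known from the documents. The 0.4 to 1.2 points and 6% to 26% error rest on assumed correlations, 50% retention and selection in Active alone. A reader might infer that the completers comparison must favour Active. The documents do not support that, since equal selection leaves error near 2.5% and selection in Sham alone works against Active.

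The undecided missing-data method is a second, smaller defect, because one permitted option is invalid. The 10% rule is incomplete: it has no reference quantity and no stated other branch. It costs clarity or power rather than type I error control, and its ITT branch leads back to completers.

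**What to change.** - Define the ITT set as all randomised participants, analysed in the assigned arm regardless of completion or device use, and use every available Day 30 PSQI.
- Pre-specify one primary missing-data method using baseline and Day 14 PSQI. A mixed model or multiple imputation would serve. Add a sensitivity analysis for data missing not at random.
- Delete single mean imputation and case deletion as options for the primary analysis.
- Delete the 10% rule: ITT is always primary and per-protocol always supportive.

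The cost is SAP wording and modest programming. Day 14 PSQI is already collected (Protocol 6.10) and data up to withdrawal are kept (8.1), although the documents do not say how many leavers would have reached Day 14. The estimate and power may be less favourable than among completers if those who leave benefit less. In the case worked above where half leave and gain nothing, the effect is 1.5 points and power about 64% at 120 per arm. The sponsor should accept that knowingly, because it is the effect in everyone randomised.
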